### **3 STUDY OBJECTIVES**

The primary objective of this clinical investigation is to evaluate the accuracy of using Masimo's INVSENSOR00026 Pulse CO-Oximeter and Sensor to measure hemoglobin, as compared to hemoglobin measurements obtained from various lab analyzer(s) and point of care device(s).

### **4 STUDY DESIGN**

#### **4.1 General Design**

This is a multi-center, prospective, nonrandomized study design. Subjects will be tested in a clinical setting. For each sample point, the SpHb value from the Masimo device will be compared to the hemoglobin value from an arterial blood draw measured by one or more reference laboratory methods. [REDACTED]

[REDACTED]

[REDACTED]

#### 4.2 Study Endpoint

Accuracy will be reported as the root mean squared error ( $A_{RMS}$ ) of the SpHb-tHb parameter. Per ISO 80601 Part 2-61, accuracy of existing pulse oximetry instruments will be reported using  $A_{RMS}$  standard calculations which are also applicable to SpHb testing.

$$Bias = \frac{1}{n} \sum_{i=1}^n (SpHb - tHb)$$

$$A_{RMS} = \sqrt{\frac{\sum_{i=1}^n (SpHb - tHb)^2}{n}}$$

#### 4.4 Population Base

Subjects will be healthy and non-healthy subjects older than 18 years of age. Subjects will be recruited in diversified demographics (age, gender, ethnicity, skin tone, comorbidities, etc.).

#### 4.5 Number of Subjects

There will be up to 300 subjects enrolled into this study. The anticipated duration of subject participation in this study will be approximately 1-2 hours in the clinic and up to 72 hours from the time subject leaves the clinic, if subject receives an arterial blood draw. The study enrollment period is expected to be approximately 3 months.

#### 4.6 Inclusion Criteria

- 18 years of age or older
- Subject has given written informed consent to participate in the study

#### 4.7 Exclusion Criteria

- (\*) Pregnant or positive human chorionic gonadotropin (hCG) test
- (\*) Any severe coagulopathy, chronic bleeding disorders (i.e., hemophilia) or recent thrombolysis
- (\*) Hemoglobinopathies and synthesis disorders (i.e., sickle cell, thalassemias, etc.)
- (\*) Subjects who are currently taking anticoagulant medication
- (\*) Subjects with allergies to lidocaine, Pain Ease, latex, adhesives, or plastic
- (\*) Subjects with skin abnormalities at the planned application sites that may interfere with sensor application, per directions-for-use (DFU) or trans-illumination of the site, such as psoriasis, eczema, angioma, burns, scar tissue, substantial skin breakdown, nail polish, acrylic nails, infections, abnormalities, etc.
- (\*) Subjects unlikely to be able to refrain from excessive motion during data collection. Excessive motion includes postural changes, making hand gestures, involuntary muscular movements, etc.

- (\*) Subjects with elevated blood pressure, skin or wrist abnormalities that may interfere with an arterial blood draw as determined by investigator or research medical staff.
- (\*) Subjects who intend on participating in heavy lifting, repetitive movement of their wrist (including riding a motorcycle) or exercise (working out, riding a bike, etc.), or any activity that will put additional stress on the wrist within 24 hours following a study involving an arterial blood draw
- Subjects deemed not suitable for the study at the discretion of the investigator or research medical staff

Note: (\*) May be self-reported by subject

## **5 STUDY PROCEDURES**

### **5.1 Subject Recruitment and Screening**

Subjects may be recruited for the study from the physician's clinical practice or by advertisement. Information to be disseminated to subjects and any advertisements will be approved by the IRB. Once a potential subject sees the recruitment material (i.e. advertisement) they can contact the clinical site to schedule an appointment. Potential subjects may also be identified by review of the site's appointment schedule for subjects that may be eligible for the study. Potential subjects may be contacted by phone by study staff using the IRB-approved phone recruitment script.

Subjects will be screened to determine their potential eligibility and interest in a study. Subjects' potential eligibility can be evaluated during their routine intake at the clinic when health history and other information are gathered for their pre-existing appointment with the clinic, or during the recruitment phone call. All subjects screened will be documented on the Screening and Enrollment log.

Subjects are considered enrolled in the study once the subject has signed and dated the informed consent. Subjects must also meet all of the inclusion criteria and none of the exclusion criteria. If the subject signs the Informed Consent form and is identified later as failing to meet all eligibility criteria, the subject will be classified as a screen failure. Upon determination that the subject does not qualify for enrollment, the reason for the subject's screen failure status will be documented on a Screening and Enrollment Log, in order to minimize bias. In case a subject leaves the study prematurely, another volunteer may be recruited.

### **5.2 Informed Consent**

The Investigator(s) and/or staff delegated for this task are responsible for conducting the informed consent process and for obtaining written informed consent, including HIPAA and the California Experimental Subject's Bill of Rights, prior to each subject's inclusion into the study. The Investigator shall not allow subjects to participate in the study or consent any subjects prior to receiving IRB approval of the informed consent form. Subjects must provide written informed consent prior to being enrolled in the study, in accordance with applicable federal and state regulations.

- 5.2.1 Following identification of a potential eligible subject as defined by the inclusion and exclusion criteria, the subject will be approached by the study staff, who will thoroughly explain the purpose, procedures of the study in respect to subject's involvement and responsibilities, potential risks & benefits, subject's rights & privacy of the data collected, and that participation is voluntary.
- 5.2.2 If the subject expresses interest in participating in the study, they will be asked to read the written informed consent approved by the local IRB and Sponsor.
- 5.2.3 Subject will be given adequate time to ask questions regarding the study and to discuss with family and friends before making a decision. Once all questions have been answered and the informed consent signed, the subject will be enrolled in the study. If the subject refuses to participate, they will not be enrolled in the study.
- 5.2.4 The Investigator shall retain a copy of the signed informed consent document in each subject's record and provide a copy to the subject.

---

## Spot-Check Noninvasive Hemoglobin (SpHb) Clinical Validation of INVSENSOR00026 TORR0003 Version 2.0

---

The Investigator is also responsible for ensuring any new information related to the study will be provided to the subject. Subject may need to be re-consented to continue participation as required by IRB.

### 5.3 Study Procedure

Operators conducting tests shall be health care professionals. [REDACTED]  
[REDACTED]

#### 5.3.1 Verification of Eligibility and Subject Demographics

- 5.3.1.1 All subjects will be asked to complete a Health Assessment Questionnaire that will be reviewed and discussed with a medical staff. If the subject does not meet all eligibility criteria, they will be notified and removed from the study.
- 5.3.1.2 Females will be asked to take a urine pregnancy test. If the subject declines the pregnancy test or if the pregnancy test is positive, the subject will be notified and removed from the study.
- 5.3.1.3 An Allen's test will be performed to determine adequate blood flow to the hand. Results will be noted on the CRF. If the Allen's test is negative, the subject will be notified and removed from the study.
- 5.3.1.4 Subject's demographic information (including, but not limited to, age, weight, height, race, ethnicity, [REDACTED], and medical history) will be recorded on CRF.

#### 5.3.2 Set-up for Noninvasive Readings and Blood Draws

- 5.3.2.1 The subject's vital signs will be monitored with FDA-cleared monitors, such as pulse oximetry, ECG, and blood pressure monitor throughout the procedure. Data captured from these safety monitors may be manually recorded by medical staff or electronically recorded. Study procedures will be immediately discontinued if the subject shows signs of discomfort or distress, indicates his/her desire to discontinue with study participation, or upon discretion of the clinical or research medical staff.
- 5.3.2.2 Subjects will be offered a snack (e.g. granola bar) and/or beverage (e.g. water, juice) prior to having any measurements collected or blood drawn.
- 5.3.2.3 Subjects will be [REDACTED] during noninvasive readings and blood draws.
- 5.3.2.4 [REDACTED]  
[REDACTED].
- 5.3.2.5 [REDACTED]
- 5.3.2.6 [REDACTED]

#### 5.3.3 Noninvasive Readings

- 5.3.3.1 Sensor should be placed on the appropriate finger(s), following manufacturer's Directions for Use and study procedure manual, and then connected to Pulse CO-Oximeter to perform noninvasive measurement.
- 5.3.3.2 Noninvasive measurements will be performed by following instructions included in the study procedure manual.
- 5.3.3.3 At the end of measurement, study data will be recorded on the CRF.
- 5.3.3.4 [REDACTED].

#### 5.3.4 Blood Draws

Individuals who perform the capillary and/or arterial blood draw(s) will be qualified health professionals. Arterial blood draws will be performed by registered nurses, certified registered nurse anesthetists, or doctors/anesthesiologists. Capillary and/or arterial sampling and handling procedures will follow accepted blood collection practices.

- 5.3.4.1 Subjects will have, at most, two attempts per capillary and/or arterial puncture.
- 5.3.4.2 Blood samples will be collected [REDACTED]. Not all blood sampling sites may be done for each subject.
- 5.3.4.3 Arterial samples should be obtained [REDACTED]. Approximately [REDACTED] of blood may be collected. Blood samples will be collected into vacuum sealed tubes containing di-potassium ethylenediaminetetraacetic acid (K2 EDTA).
- 5.3.4.4 A capillary sample should be obtained [REDACTED]. Approximately one or two drops of blood may be collected from each sampling. [REDACTED] results will be recorded on the CRF.
- 5.3.4.5 For arterial blood draws, lidocaine injection and/or topical anesthetic may be used to numb the site where the needle is inserted into the radial artery. Subjects will be given the option to receive or decline local anesthetics. An ultrasound may be used to visualize blood vessels and guide the placement of the needle for the blood draw. After the blood sample has been collected, firm, constant pressure should be maintained on the puncture site for at least 5 minutes to ensure that the bleeding has stopped.
- 5.3.4.6 Total blood withdrawal will be approximately [REDACTED] total of blood, allowing for sample collection/or handling issues.

#### 5.3.5 Blood Analysis

- 5.3.5.1 Blood tube(s) will be identified with a unique barcode [REDACTED] for processing and additional analysis.

#### 5.3.6 Study Completion

Study completion is defined as when the subject has completed the noninvasive device readings and blood draw(s).

- 5.3.6.1 The sensors will be removed and the skin inspected for signs of redness or irritation.
- 5.3.6.2 Subjects will be offered a snack (e.g. granola bar) and/or beverage (e.g. water, juice).
- 5.3.6.3 Subjects will be allowed to leave after medical personnel determine it is safe to do so. Subjects will be encouraged to remain in the study area until they feel fit to leave.
- 5.3.6.4 Vital signs (including heart rate and blood pressure) will be recorded for subject safety monitoring before subject exits the study.
- 5.3.6.5 Subjects will be given post-care instructions for arterial blood draws.
- 5.3.6.6 Subjects who received an arterial stick will be instructed to contact the principal investigator in the event of any potential adverse event up to 72 hours after being discharged from the clinic. AE(s) will be recorded on the CRF and/or Adverse Event Report Form.

#### 5.4 **Early Withdrawal of Subjects**

##### 5.4.1 Withdrawal of Individual Subjects

Subjects can withdraw from the study at any time for any reason if they wish to do so without any consequences or loss of benefits to which they are otherwise entitled. Subjects may also be withdrawn from the study at any time prior to expected

completion at the discretion of the Principal Investigator or research medical staff for safety concerns, failure to adhere to protocol requirements, malfunction that prevents accurate collection of data, sampling errors, inability to collect noninvasive device and/or hemoglobin readings, administrative reasons, etc.

Any data collected until the time of subject withdrawal may be included in the final data analysis. Information on the subject's withdrawal should either be documented in the medical record or on the CRF and should include clear documentation of the reason for withdrawal to the Sponsor.

No follow-up is required for subjects who did not receive an arterial stick and are withdrawn from the study, as there are no long term effects anticipated from participating in this study. Subjects who received an arterial stick will be instructed on wound care and to contact the principal investigator in the event of any potential adverse event up to 72 hours after being discharged from the clinic. AE(s) will be recorded on the CRF and Adverse Event Report Form.

Subjects that withdraw from the study may be replaced by another volunteer.

## 6 STATISTICAL PLAN

[REDACTED]

### 6.1 Sample Size Determination

#### 6.1.1 Earlier Studies

Earlier studies of Pulse CO-Oximeters using similar technology were used to provide estimates of the required variances used in the sample size calculation. In the earlier study, the variability of both the test (SpHb) and the reference method ( [REDACTED] ) method were calculated. [REDACTED]

[REDACTED]

#### 6.1.2 Deming Regression

Since the reference method has a measureable variation, Deming regression is indicated. (Pasing Bablok regression is an alternate regression method for data with variation in the reference method, however, it is not necessary to run both procedures.) [REDACTED]

[REDACTED]

#### 6.1.3 Effect Size

It is desired to determine if the slope of the Test on Reference regression is significantly different than [REDACTED]. All regression lines will pass through the mean point. Therefore, the slope and intercept terms are not independent and it is only necessary to check if the slope is significantly different than [REDACTED]. The levels of significance were set at [REDACTED]

[REDACTED]

For a slope range between [REDACTED], and a mean data point of [REDACTED] the intercept term will be between - [REDACTED]. Additional input constants used in the calculations are shown in Table 1 for both the Deming Slope and Deming Intercept.

Additional input constants used in the calculations are shown in Table 1 for both the Deming Slope and Deming Intercept.

██████████	██████
██████	██████
██████████	██████
██████████	██████
██████████████████	██████
██████████████████	██████
██████████████████	██████
██████████████████	██████

██████████

**6.1.4 Monte Carlo Simulation**

The data from the earlier study contained data from ██████████. This data was resampled by Subject (with replacement) to simulate data sets with differing numbers of Subjects.

A Deming regression was calculated for each of ██████ iterations. The Slope and Intercept from each regression were stored and the statistics required to meet the effect size requirements were calculated for each level of subjects. These simulations indicated that the Slope effect size of ████████████████████. Similarly, ██████████ would be required to meet the Intercept requirement. The initial sample size, assuming the measurements are all independent, is set to ██████████

The initial sample size, assuming the measurements are all independent, is therefore set to ██████████

**6.1.5 Intraclass Correlation Coefficient**

Since this protocol will be run in several clinical sites, an evaluation of the Intraclass Correlationiii was performed. Based on the Site to site variation seen in the earlier study, the Between Site variance component was ██████. The Across Site variance was calculated as ██████. The ICC is found by:

$$ICC = \frac{AcrossSiteVariance}{AcrossSiteVariance + BetweenSiteVariance} = ██████$$

This gives a Sample Size Inflation factor of:

$$██████████████████$$

Therefore, this study will use a minimum of ██████████ total subjects. Additional subjects may be required to fill in demographic bins or account for subject drop out of ██████

In order to collect data across multiple subject health conditions, █ sites will be utilized. The number of subjects per site will be determined by patient availability and patient demographics at each site. This will ensure that other study endpoints related to the distribution of observed hemoglobin values are also met.

Final statistical analysis will be performed on a population set who have enrolled and completed the study procedure as defined per the protocol.

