These routine CBC tests are invasive, intermittent, increase infection risk to patient, and can expose a clinician to the risk of infection via blood borne pathogens. In addition, multiple blood tests at hospitals have been attributed to patients developing hospital acquired anemia (HAA). A recent study looked at more 17000 myocardial infarction patients across 57 US hospitals and found 20% of the patients had developed HAA over their hospital stay.

Recent advancements in pulse oximetry technology have led to the development and FDA-approval of a multi-wavelength Pulse CO-Oximeter, designed for continuous, noninvasive measurement of total hemoglobin concentration (Masimo SpHb™ technology). Thus, noninvasive measurement of total hemoglobin fortify a clinician's toolkit and can potentially offer a great clinical value and provide a simple, portable, safe and accurate method for monitoring patients.

[figure not shown]
To evaluate the accuracy of hemoglobin measurement, data collection and analysis of blood should be conducted in a controlled manner to reduce variability between noninvasive hemoglobin readings to the hemoglobin value obtained from a reference sample. Small differences in the processing and/or handling of hemoglobin may have dramatic effects in analytical reliability and reproducibility. Therefore, potential bias and confounding factors should be minimized as much as possible by having consistent technique of clinician, posture of the donor, timing of samples, etc.

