#### 6.3.2 Regression Analysis

6.3.2.1 Data will be randomly resampled to provide a uniform distribution of data points across the measurement range.

6.3.2.2 To account for variation in the reference tHb values, Deming linear regression analysis will be calculated.

6.3.2.3 Estimates of standard deviation in both the SpHb and tHb data (required by Deming regression) will be calculated from earlier studies [REDACTED]

6.3.2.4 Estimates and 95% confidence intervals for both Y-intercept and Slope will be calculated for a Deming regression across all [REDACTED] sites and within each site individually.

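### The all-site Deming slope has no visible site term, although the site mix is the stated route to the hemoglobin distribution, so a site offset that tracks mean Hb could bias it

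*Combined protocol and SAP*

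**What the plan says.** Section 6.1.5 gives the reason for having several sites: "In order to collect data across multiple subject health conditions". It leaves the allocation open: "The number of subjects per site will be determined by patient availability and patient demographics at each site". It then presents this as the way the Hb distribution is obtained: "This will ensure that other study endpoints related to the distribution of observed hemoglobin values are also met". No visible text requires any one site to span the Hb range.

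The same section acknowledges that sites differed before: "Based on the Site to site variation seen in the earlier study, the Between Site variance component was" (the figure is blacked out). The visible use of that variation is an inflation factor for the sample size. Section 1.1 warns in general terms: "Small differences in the processing and/or handling of hemoglobin may have dramatic effects in analytical reliability and reproducibility".

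The study is sized on a Deming slope. Section 6.1.3 states the aim: "It is desired to determine if the slope of the Test on Reference regression is significantly different than" (value blacked out). Section 6.1.4 describes the simulation: "This data was resampled by Subject (with replacement) to simulate data sets with differing numbers of Subjects". Resampling by site is not described.

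For the analysis, 6.3.2.4 says: "Estimates and 95% confidence intervals for both Y-intercept and Slope will be calculated for a Deming regression across all" sites, and it adds a separate fit within each site. Section 6.3.2.1 first resamples the data to a uniform spread over the measurement range, with no mention of site. Section 6.3.1 plans Bland-Altman plots by site and a correction for site clustering, stated for that analysis only. The accuracy endpoint in 4.2 and 6.2.1 is A_RMS.

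**The concern.** The pooled slope is meant to show whether the device reads proportionally across the Hb range. If much of that range comes from differences between sites, a constant local offset (operator technique, sample handling) at a site with low or high mean Hb enters the slope as though it were device error. The slope could then suggest range compression or expansion in a device that has neither, or mask a real one if the offset runs the other way.

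Inflating the sample size for the intraclass correlation does not remove this. More subjects narrow the interval around a biased slope. If offsets are random rather than aligned with Hb, the slope is right on average, but an interval that ignores site is too narrow.

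**Working it through.** **No figure of the plan can be reproduced.** The slope effect size, significance level, simulated sample size, variance components, inflation factor and number of sites are blacked out. The ceiling of 300 subjects (4.5) has no visible derivation. The inputs below are therefore assumptions, except the total of 300.

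**Formula.** With a constant offset at each site, the pooled slope shifts by approximately

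shift = Cov_between(site mean Hb, site offset) / Var_total(Hb), where Var_total = Var_between + Var_within.

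The shift is zero if site means are equal, or if offsets are uncorrelated with site mean Hb.

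**Set A: two sites of 150.** Within-site Hb SD 1.2 g/dL, SpHb error SD 0.9, reference error SD 0.2, true slope 1.00, offset at the low-Hb site. Simulated with 1,000 runs per case.

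| Hb gap | Offset | Formula | Simulated pooled slope (SE) |
|---|---|---|---|
| 4 | 0.5 | 1 − (2 × 0.25)/(4 + 1.44) = 0.908 | 0.907 (0.022) |
| 4 | 0.25 | 1 − (2 × 0.125)/(4 + 1.44) = 0.954 | 0.954 (0.023) |
| 2 | 0.5 | 1 − (1 × 0.25)/(1 + 1.44) = 0.898 | 0.898 (0.034) |
| 2 | 0.25 | 1 − (1 × 0.125)/(1 + 1.44) = 0.949 | 0.950 (0.034) |
| 0 | either | 1.00 | 1.00 |

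In the first row the distance from 1 is 0.093/0.022, about 4 SE. The slope fitted after centring SpHb and tHb within site is 1.00 in every row, with SE about 0.045.

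Precision check at gap 4. The combined error SD is √(0.81 + 0.04) = 0.922. The pooled SE is 0.922/√(300 × 5.44) = 0.023. The site-centred SE is 0.922/√(300 × 1.44) = 0.044. Centring about doubles the SE.

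**Set B: three sites of 100.** Within-site Hb SD 1.3, same error SDs, 600 to 1,500 runs per case. Offsets rise with site mean Hb. Adjacent sites differ by m in mean Hb and by o in offset, so the shift is (2/3)mo / ((2/3)m² + 1.69).

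| m | o | Formula shift | Simulated pooled slope | False rejection of slope 1 |
|---|---|---|---|---|
| 0 | 0.5 | 0 | 1.01 | 5% |
| 1 | 0.25 | 0.07 | 1.07 | 50% |
| 1 | 0.5 | 0.14 | 1.14 | 97% |
| 2 | 0.25 | 0.08 | 1.08 | 83% |
| 2 | 0.5 | 0.15 | 1.16 | 100% |

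- *Direction.* Reversing the offsets in the last row gives 0.85.
- *Masking.* With m = 2 and o = 0.25, a true slope of 0.85 reads 0.93, and detection falls from 100% to 82%.
- *Uniform resampling as in 6.3.2.1.* In the last row the slope is still 1.14.
- *Random offsets, SD 0.3.* The mean slope stays at 1.00. Its SD rises from 0.035 to 0.073 (m = 1) and from 0.025 to 0.067 (m = 2). An interval that ignores site then rejects a true slope of 1 in 33% and 46% of runs, against 6% when site means are equal.

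The site-centred slope recovers the true value throughout, to within simulation error.

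**What the planned site-level analyses would show (Set A, gap 4).** The difference in mean bias between two sites has SE 0.922 × √(2/150) = 0.106. An offset of 0.5 is about 4.7 SE and an offset of 0.25 about 2.3 SE. The simple average of the two planned per-site slopes is 1.00 with SE about 0.045, equivalent to the site-centred slope. One site alone gives an SE of 0.922/√(150 × 1.44) = 0.063. With 100 subjects under Set B it is about 0.07.

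**The case against.** The strongest reply is that the plan already contains the remedy's ingredients. Per-site Deming slopes with intervals are planned, and averaging them gives what a site-centred fit gives. The by-site Bland-Altman plots would usually expose a 0.5 g/dL offset. This stands, and it rules out saying that the problem must stay hidden. It leaves a gap, however. No visible rule combines the per-site slopes or says what follows when they conflict with the pooled slope, and nothing in these displays corrects the pooled slope or its interval.

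A reader might infer that each site supplies its own Hb level, so that the pooled slope will be wrong. The documents do not say so. Hb by site is not given, section 4.4 plans varied recruitment, section 5.1 allows advertisement, and section 6.1.5 mentions demographic bins. With equal site means the slope is unaffected. Blacked-out text in 4.1, 6, 6.1 and 6.3.2.3 may also hold a site term or a per-site target. Set A at a 4 g/dL gap, with the offset fully aligned to Hb, is near the worst case.

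A reader might also infer that the site-centred slope should simply replace the pooled one. That is unsafe. With no site offset, but a device that over-reads by 0.5 g/dL below 12.3 g/dL, the pooled slope was 0.907 (about 4 SE from 1) and the site-centred slope 0.96 (under 1 SE). Centring then conceals a real device error.

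Finally, the regression is listed in 6.3 among additional analyses, beside an A_RMS endpoint. That limits the weight of the point but does not remove it, because 6.1.3 and 6.1.4 size the study on the slope.

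**Conclusion.** The point holds in conditional form. The plan relies on the site mix for its Hb distribution and acknowledges site-to-site variation, yet shows no site term in the all-site Deming fit. If site mean Hb differs, offsets of 0.25 to 0.5 g/dL that track it move the pooled slope by about 0.05 to 0.16 in either direction, and random offsets of SD 0.3 raise false rejection from about 5% to between 33% and 46%. These sizes rest on assumed site numbers, Hb gaps, error SDs and offsets; the plan's own values are blacked out.

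The conclusion concerns the interpretation of the slope and its interval. It does not extend to the A_RMS calculation, and the documents do not establish that the pooled slope will in fact be biased.

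**What to change.** In 6.3.2.4:

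1. Report, beside the pooled slope, a common within-site Deming slope (SpHb and tHb centred by site) with a 95% confidence interval.
2. Tabulate mean Hb and mean bias by site.
3. Use an interval for the pooled slope that allows for site.
4. State that if the two slopes disagree, proportional error of the device cannot be separated from site offset, and that no conclusion will be drawn from either slope alone. Define disagreement beforehand, most simply as the two intervals leading to different conclusions about the slope.

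The cost is one extra regression, one small table and a few sentences of plan text, with no added subjects. The downside is a wider slope interval: about double for the centred slope in the illustrative case (SE 0.045 against 0.022). With few sites, the site-allowing interval for the pooled slope may also be wide.

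A quota asking each site to recruit part of its subjects outside its usual Hb group is optional and not part of this fix. In Set A at gap 4 and offset 0.5, a two-way exchange of 25% brings the pooled slope to about 0.955. Adding only normal-Hb adults at the low-Hb site brings it to about 0.93.
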